The present study will test this hypothesis on a group of patients with MDD non-responders to standard TMS by conducting pre-treatment functional connectivity to enable targeting of rTMS based upon individualized connectivity maps. These locations will then be used at the NYSPI site and also given to the treating physician ([name]) to optimize target for focal brain stimulation and efficacy across individuals. Of note, patients from group 1 will be scanned at the NYSPI site but will not receive treatment here, whereas group 2 will both be scanned and receive treatment.

Our preliminary data in Fig. 1 shows results acquired from a subset of patients with MDD that reveals an increase in anti-correlation between left-DLPFC and sgACC consecutive to convulsive therapy. These results suggest that ability to deliver TMS pulse to special targets identified on functional connectivity maps (e.g. DLPFC) have the potential to positively confirm their involvement in MDD. Increase in anticorrelation of rsFC signal of these regions after TMS would amount to such evidence. This is exactly what we observed in convulsive therapy as is shown in Fig 1 in which green-blue-purple spectrum on the sgACC rsFC maps are the surface vertexes within BA46 with highest anticorrelation BOLD signal with sgACC. We seek to replicate this effect with targeted TMS in non-responders to standard TMS. Such strategy has the potential to optimize therapeutic efficacy of TMS (see Fig. 1, attached).

Our justification for committing the non-responders to a second cycle of TMS is as following:

- 1) The second cycle will use an entirely different type of TMS, i.e. neuronavigated TMS based on the functional connectivity maps obtained from patients' brain which offers, hereto-forth, the best guide for the efficacy of TMS as shown in Fig. 1.

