- 2) Since the patients for the second cycle are randomized to receive either neuronavigated or standard TMS, we can justify a second cycle of standard TMS by statistics from [name] clinics which are in agreement with application guidelines for the use of TMS (Rossi et al., 2009). As for [name] past experience is concerned, of the 139 patients that received 9 weeks of TMS, 60 responded at the 4 week point and 89 responded at the 8 week point. Of the 79 that did not respond at the 4 week measurement, 42 (more than 50%) responded at the week 8 point. Response is defined here as a 50% or greater reduction in starting Ham D score. As such, while the advantage of the second round of TMS is clear for the patients who receive neuronavigated TMS, even for the patients who receive the second round of standard TMS the above facts demonstrate the advantages of prolonged (4-8 week) treatment by TMS in the form of a 50% favorable outcome in that group of patients.

In addition to resting state functional connectivity, we will also assess glutamate (Glu) concentrations and resting-state cerebral blood flow/volume (rsCBF/rsCBV) in DLPFC and cortical midline structures (CMS) using Magnetic Resonance Spectroscopy (MRS) and Arterial Spin Labelling (ASL), respectively. CMS refer to brain structures situated near the medial wall of the brain and is mainly comprised of the ventral medial prefrontal cortex, dorsal medial prefrontal cortex, anterior cingulate cortex (the supragenual part in particular) and posterior cingulate cortex. Regional increases in Glu release increase the metabolic rate of post-synaptic neurons (28), and surrounding astrocytes (29), leading to regional BOLD signal increases (30). Glu concentrations may therefore be linked to overall functional connectivity patterns (31-34). In particular, Glu levels in left DLPFC in MDD provide an index of local metabolic activity, and abnormalities can be reversed in a dose-dependent manner by rTMS (35). These effects are present not only close to the stimulation site (left DLPFC), but also in remote (right DLPFC, left cingulate cortex) brain regions.

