At NYSPI or at CBIC (Citigroup Biomedical Imaging Center at Weill Cornell Medical College) MRI facility all patients will come to have a brief conversation with [name] to verify eligibility to participate in this study, and to complete fMRI scans. **Clinical assessments pre/post TMS treatments will be implemented at Contemporary Care or NYSPI.** Patients will complete some assessments using StudyTrax.

Group 1 are patients coming from [name] offices who will be scanned at the NYSPI or CBIC MRI Unit pre/post TMS treatments. TMS treatments for this group will be implemented under [name] protocol and WIRB. Group 2 are patients coming from [name] offices who will come to the NYSPI or CBIC site to be scanned at the NYSPI or CBIC MRI Unit pre/post TMS treatments. **A second course of TMS will be implemented at any of [name] offices (only). For both, Group 1 and Group 2, we will be doing the scanning only (at NYSPI or CBIC)** (Table 1. Timing of all Study Procedures attached). **No treatments will be implemented at NYSPI.**

Overview of Study Design:

Patients from [name] offices will be divided in 2 groups. Group 1 (N=30) will be depressed patients undergoing standard TMS for the first time. Group 2 (N=30) constitutes those who have previously demonstrated that they do not respond to standard TMS. MDD patients prescribed to receive standard TMS for the first time (group 1) will have resting-state FMRI in order to see if we can predict their responsiveness based on the functional connectivity maps. Non-responders to standard TMS approaches (Group 2) will be randomized (3:2) to either receive targeted (N=20) or standard (N=10) repetitive TMS (rTMS) treatments. A connectivity-based targeting strategy will be used on patients undergoing targeted

rTMS to optimize target for focal brain stimulation. Response is defined as a 50% or greater reduction in starting HDRS score. Raters and patients in group 2 will be kept blinded to the treatment assignment. All patients referred from the ongoing treatment study will be assessed by 3 tesla brain MRI, MRS and CBF/CBV procedures at baseline and immediately following the final treatment. **At NYSPI we will only do the imaging component. All treatments will be implemented at any of [name] offices.**

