Patients from group 1 will be scanned at the NYSPI or CBIC MRI Unit pre/post TMS treatments. TMS treatments for this group will be implemented under [name] protocol and WIRB. Patients from group 2, will receive another cycle of standard versus targeted TMS, 5 times a week for 6 weeks (30 treatments), followed by a taper phase of 6 sessions to cover 3 treatments in week 1, 2 treatments in week 2 and 1 treatment in week 3. For these patients, second visit to NYSPI or CBIC will occur after first cycle finishes and right before second cycle begins. Also will receive a second post-TMS scan after second cycle finishes (see Diagram 3). Patients will be classified as responders to TMS with at least 50% decrease in HDRS-24 scores from baseline. Patients will be classified as non-responders to TMS with less than 50% decrease in HDRS-24 scores from baseline.

Screening:

A phone screen will be used for this study (NT TMS Screening Phone call Script attached). Patients will come to the NYSPI to meet with [name] to verify eligibility, and after the patient signs the informed consent form and the HIPAA authorization, will undergo clinical assessments to assure adherence to all inclusion and exclusion criteria. Eligible patients will be enrolled in the study.

[name] will explain to patients that at NYSPI they will only come for the imaging component and that no treatments will be implemented at the NYSPI site.

MRI, MRS and CBF/CBV Scanning:

Subjects will undergo 3 tesla (3T) brain MRI-MRS-CBF/CBV scanning. None of the imaging modalities used in the study will include exogenous contrasts. MRI scans will be performed at the NYSPI or CBIC MRI facility immediately before and after the rTMS treatment. 1H MRS PRESS TE80, ASL, FSPGR, resting state MB EPI (BOLD) will be performed at 3T. [name] will be responsible of Multiband EPI, PRESS and ASL for this study. To identify coordinates in the left DLPFC we will use functional connectivity (FC) seed based analysis centered on left DLPFC ROIs to identify the site (X) with peak anticorrelation with the sgACC.

DLPFC Mapping for targeted TMS (for group 2):

Targets for focal brain stimulation with repetitive TMS will be modified based on the MRI. Methodology as follow:

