I. The subgenual region of interest (ROI) was constructed by placing a 5 mm radius sphere at MNI coordinates (6, 16, -10), masked to include only sampled grey matter voxels. These subgenual coordinates were chosen based on prior studies where a reduction in subgenual activity was associated with antidepressant response across a wide range of treatment modalities (Fox et al., 2012). Resting state functional connectivity across 500 healthy right-handed subjects from the Human Connectome Project data release (<http://www.humanconnectome.org/data/>) was used for initial analyses as an independent cohort to

construct an average group-level functional connectivity map. The entire subgenual functional connectivity map generated from this independent cohort was used as a mask to extract the average time course activation from each MDD patient.

II. Use Matlab software to generate spheres of varying radii on T1W anatomical images centered on node coordinates within the left DLPFC to account for varying focality of different potential cortical stimulation sites. This procedure will include the mapping of ROI spheres to the surface of MNI space, extract the time series courses and compute the correlation with the subgenual functional connectivity map to find the ROI with the highest anticorrelation value (X) that could serve as optimized target for focal brain stimulation. Next, we will warp the best ROI (X) into the subject native volume space for neuronavigation of TMS coil.

TMS Treatments (for group 2):

All standard TMS treatments for group 1 will be implemented at any of [name] offices.

Second cycle of TMS treatments for group 2 will be implemented at any of [name] offices.

Subjects of this group will be randomized to either receive standard versus navigated TMS (3:2). Patients will receive a total of 36 TMS treatments, 5 times a week for the first 6 weeks (30 treatments), followed by a taper phase go 6 sessions to cover 3 treatments in week 1, 2 treatments in week 2 and 1 treatment in week 3.

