Using the NeuroStar Therapy System, the subject's motor threshold (MT) will be determined and the coil placed over the left DLPFC guided by Brainsight Neuronavigation device, which uses MRI images loaded into the system to navigate the coil over the target within the DLPFC. All patients from group 2 will receive stimulation over the left DLPFC at 120% of the MT at a frequency of 10Hz; for a total of 3,000 pulses per session. A total of 36 treatment sessions will be provided over 9-weeks. **All treatments will be implemented outside the NYSPI.**

The NeuroStar TMS Therapy System is the first TMS device cleared by the U.S. Food and Drug Administration (FDA) to treat patients with Major Depressive Disorder (MDD) who have not benefited from antidepressant treatment. Treatment parameters in this study will follow FDA approval, i.e. stimulation pattern, time course, device and patient population. The "standard" procedure of coil positioning locates the left DLPFC at 5-cm anterior to the "hand motor hotspot" along the curvature of the scalp. Alternate stimulation site within the DLPFC in each patient will be used to personalize treatments based on their rsfMRI, therefore its application is considered off-label. Please find IDE Decision Worksheet in additional documents related to this study (uploads section).

Brainsight for TMS:

Brainsight is what is generally referred to as a neuronavigator (also often called a frameless stereotaxy device). Its main function is analogous to a GPS, but applied to the brain. The device takes as input, the structural MR images of the subject, and using an infrared position sensor and related accessories, maps the location and orientation of a TMS coil held on the subject's head to the images and displays a representation of the coil on the images.

This provides two important functions. First, it displays a live representation of the coil on the images on the computer screen, allowing the operator to accurately use the MR images (and the anatomy shown by the images) to determine the location of the coil on the subject's head. Second, fMRI images may be overlaid

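### The protocol is inconsistent on whether the standard arm of Group 2 is neuronavigated, and its patient-blinding statement depends on the answer

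*Protocol*

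**What the plan says.** All places are in the protocol.

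- **Blinding.** Study Procedures, Overview of Study Design: "Raters and patients in group 2 will be kept blinded to the treatment assignment". The same paragraph defines the population: "Group 2 (N=30) constitutes those who have previously demonstrated that they do not respond to standard TMS". Inclusion criterion 12 for this group requires non-response to rTMS within the current episode.
- **Arm labels.** Background, Significance and Rationale, second item of the justification for a second cycle: "Since the patients for the second cycle are randomized to receive either neuronavigated or standard TMS". TMS Treatments (for group 2): patients are "randomized to either receive standard versus navigated TMS (3:2").
- **Second cycle as a whole.** First item of the same justification: "The second cycle will use an entirely different type of TMS, i.e. neuronavigated TMS based on the functional connectivity maps". No arm is named.
- **Coil placement.** TMS Treatments (for group 2): "coil placed over the left DLPFC guided by Brainsight Neuronavigation device". This is not limited to an arm, and the following sentence, on intensity, frequency and pulses, covers every Group 2 patient.
- **Standard positioning.** The next paragraph defines it as a point measured on the scalp, 5 cm forward of the motor hotspot. Navigation is not mentioned.
- **Target derivation.** The only procedure for deriving a navigation target is headed "DLPFC Mapping for targeted TMS (for group 2").
- **Equipment.** Brainsight for TMS describes an infrared sensor with accessories, a live screen display and continuous head tracking.
- **Ratings.** Study Procedures allows assessments before and after treatment at either Contemporary Care or NYSPI. Criteria for Early Discontinuation places weekly HDRS-24 during the second course at the treating offices. Assessment Instruments says this study performs no independent assessments, and then lists HDRS-24 among those done at NYSPI.

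**The concern.** Standard versus targeted rTMS in Group 2 is the only randomised comparison in the protocol. Its outcome, a fall of at least half in the HDRS, comes from an interview-rated scale and so is open to expectation in both patient and rater. Blinding is the stated protection.

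Whether that protection exists for patients depends on a fact the protocol leaves unsettled: whether a standard-arm patient sees the navigator. These patients have already been through a course of rTMS, so they have something to compare the new set-up with.

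The same fact decides what the comparison tests. If navigation is confined to one arm, the contrast is navigation and connectivity target together. If both arms are navigated, it is the connectivity target alone. A reader of the results could not tell which was studied.

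**Working it through.** No power, sample-size or effect figure is involved, so the check is a comparison of texts.

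**Reading A: only the targeted arm is navigated.**
- Both places that name the arms (the rationale for a second cycle and TMS Treatments) make navigation the difference between them.
- Standard positioning is a scalp measurement and needs no navigator.
- A navigation target is derived for targeted TMS only.
- The Brainsight sentence speaks of moving the coil to a target, which at that point in the protocol only a targeted patient has.

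It follows that the arms differ in sensor, accessories, display and head tracking. The text shown describes no sham navigation and no other masking. The patient-blinding statement then has no procedure behind it.

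**Reading B: both arms are navigated.**
- The Brainsight sentence stands under a heading for the whole of Group 2, after both arms have been introduced, and the sentence after it covers all Group 2 patients.
- The first item of the justification calls the second cycle neuronavigated without naming an arm.

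Patient blinding is then feasible, because the arms differ only in stored coordinates. But the arm labels misname the contrast, and no target is defined for the standard arm. The Explain text for Device #1 adds to the difficulty: it says the 5-cm rule misses the DLPFC more than a third of the time, whereas the Brainsight sentence navigates to a target inside the DLPFC.

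**Comparison.** Reading A fits more of the text but leaves patient blinding unsupported. Reading B supports blinding but conflicts with the arm labels and lacks a standard-arm target. Neither fits every statement.

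**Raters.** Three statements bear on where and by whom HDRS is rated. Assessments before and after treatment may take place at Contemporary Care, where patients may be treated. Weekly HDRS-24 in the second course is done at the treating offices. No independent assessments are performed in this study. The NYSPI list of instruments therefore does not by itself separate raters from treatment delivery.

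**Scope.** Planned Group 2 patients: 30. Sessions per patient: 30 + 6 = 36. The inconsistency concerns the set-up at each of these.

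**The case against.** The strongest reply is that one reading fits nearly everything and the rest is loose drafting. On that view the Brainsight sentence was meant for targeted patients, since only they have a target, and the sentence on all Group 2 patients concerns intensity, frequency and pulses rather than coil guidance. Much of this stands and is why Reading A is preferred. It does not rescue the blinding statement, because Reading A is the one under which patient blinding has no described support.

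The opposite reply is that navigated is shorthand for connectivity-targeted and both arms use the device. That is plausible, but the standard-arm target is then still undefined.

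It is also fair to say that unblinding is an inference. How far a patient could guess the arm depends on what the first course looked like. That course ran under a separate protocol, and its set-up is not described. The attached tables and diagram are not shown either, and masking details could be there. This limits what may be claimed about actual unblinding. It does not remove the inconsistency within the text at hand.

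A reader might infer that the comparison is biased towards the targeted arm, because the rationale says "the advantage of the second round of TMS is clear for the patients who receive neuronavigated TMS". The documents do not support a direction. The same item also argues for repeating standard TMS, citing 42 responders at week 8 among 79 patients without response at week 4 (42/79 = 53.2%).

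**Conclusion.** The point holds as an inconsistency with a consequence for a stated design feature. The protocol asserts that Group 2 patients are blinded. On the better-supported reading of its treatment text, the procedures shown do not support that. On the other reading, the arms are misnamed and the comparator's navigation target is missing. Either way, the protocol does not fix what its only randomised comparison estimates.

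The scope is all 30 planned Group 2 patients. The bias has no computable size or direction, and none is claimed.

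Two stronger conclusions should be resisted. The documents do not show that patients were in fact unblinded, because the first-course set-up is not described. Nor do they show that rater blinding is broken: it is not contradicted, but the place of assessment does not secure it.

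The verdict assumes that the attachments not shown contain no masking procedure. If they do, the passages still need reconciling, and the blinding part of the concern would be smaller. The change should be made while enrolment is open.

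**What to change.** Reconcile the justification for a second cycle (both items) and TMS Treatments (for group 2) with the blinding statement in the Overview of Study Design, by one of two routes.

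- **(a) Same visible set-up.** State that both arms see the same Brainsight set-up. The standard-arm position is located by the protocol's existing standard procedure and recorded in the navigator under a coded label, with no change of site, dose or schedule. Rename the arms by target rather than by navigation.
- **(b) Open to patients.** State that the standard arm is not navigated, withdraw the patient-blinding statement and describe the comparison as open to patients.

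Under either route, state that the endpoint HDRS-24 is rated by existing staff who have no access to the allocation or the target file and do not attend treatment. If that cannot be met, withdraw the rater-blinding statement as well. Report how the Group 2 patients already treated were set up, since the cohort may be mixed.

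**Cost.** Route (b) is wording only. Route (a) is mainly wording if both arms are already navigated, apart from stating how the standard-arm position is recorded. Otherwise it adds some set-up time per standard-arm session, which the protocol does not allow one to quantify. Route (a) should need no new device or scan: Brainsight has already been interfaced with the NeuroStar devices at Contemporary Care, and all patients have baseline MRI. Its downside is that the comparator's coil may be held more precisely than in usual practice, which moves it somewhat away from the conventional approach the study sets out to improve on.

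### The reference signal that sets the individual TMS target is described in different ways, and the step I average, read literally, is not the sgACC signal

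*Protocol*

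**What the plan says.** Three parts of the protocol describe how the target is found.

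- **Background, Significance and Rationale** describes the preliminary maps as showing "surface vertexes within BA46 with highest anticorrelation BOLD signal with sgACC".
- **MRI, MRS and CBF/CBV Scanning** says the seed-based analysis is done "to identify the site (X) with peak anticorrelation with the sgACC".
- **DLPFC Mapping for targeted TMS (for group 2)**, step I, builds the subgenual region by "placing a 5 mm radius sphere at MNI coordinates (6, 16, -10), masked to include only sampled grey matter voxels". It then forms a group map from "Resting state functional connectivity across 500 healthy right-handed subjects" and states: "The entire subgenual functional connectivity map generated from this independent cohort was used as a mask to extract the average time course activation". Step II takes the time series of candidate left DLPFC spheres and says to "compute the correlation with the subgenual functional connectivity map to find the ROI with the highest anticorrelation value (X").

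None of these parts says whether the average is weighted by the map values, whether the map is thresholded or split by sign, or how the global signal is handled. The step matters for the targeted arm of Group 2. The Overview of Study Design has these patients "randomized (3:2) to either receive targeted (N=20) or standard (N=10) repetitive TMS (rTMS) treatments". The ratio and the counts there do not match each other, which is a separate matter; only the listed 20 is used here.

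**The concern.** The sgACC time course, an average over the whole cohort map, and a map itself are three different objects. A map is not a time series, so step II does not by itself say what the node signals are correlated with. One analyst working from the scanning section and another working from step I could compute different coordinates from the same scan.

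The literal wording of step I is also the least favourable version. A mask selects voxels, an average over a mask is ordinarily unweighted, and using the entire map rules out a threshold or sign split. The map must contain both signs: it is positive around its own seed, and the method presumes negative values in left DLPFC. An unweighted mean over it lets the two parts cancel and leaves mostly whatever is common to grey matter.

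At stake is the definition of the experimental intervention. The study hypothesis concerns individual DLPFC-sgACC connectivity, and it is tested well only if the reference is the sgACC signal or a good proxy for it.

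**Working it through.** The protocol states no figure on this point, so there is nothing to reproduce. The check is a short derivation and a simulation. **Every simulation input is an assumption**; none comes from the protocol.

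**Model.** Voxel v of the map has signal x_v(t) = w_v·s(t) + g(t) + noise. Here s is the sgACC signal (SD 1), g is a signal shared by the whole brain (SD σ), and noise has SD 1. The couplings w_v have mean m and SD 0.3 over V = 3000 voxels.

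**Unweighted mask average.** It equals m·s + g + averaged noise, so its correlation with s is about m / √(m² + σ² + 1/V).

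- m = 0.1, σ = 0.3: 0.1/√(0.01 + 0.09 + 0.0003) = 0.32 (simulated 0.31)
- m = 0.2, σ = 0.6: 0.2/√(0.04 + 0.36 + 0.0003) = 0.32 (simulated 0.32)
- m = 0.1, σ = 0: 0.1/√(0.01 + 0.0003) = 0.98 (simulated 0.98)

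**Average weighted by the signed map values.** It is about (m² + 0.09)·s + m·g, so the correlation is about (m² + 0.09)/√((m² + 0.09)² + m²σ²).

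- m = 0.1, σ = 0.3: 0.10/√(0.0100 + 0.0009) = 0.96 (simulated 0.96)
- m = 0.2, σ = 0.6: 0.13/√(0.0169 + 0.0144) = 0.73 (simulated 0.73)

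Over all settings without mean-signal removal that had a shared signal or m = 0, the simulated correlation with s was -0.02 to 0.55 for the unweighted average and 0.73 to 1.00 for the weighted one.

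**Removal of the mean signal.** If G is the mean over the mask and is regressed out of every voxel, the mean of the residuals is G − G·(G'G)/(G'G) = 0. The unweighted average then carries no information at all. This is algebra and needs no other input, but it is exact only when the signal removed is the mean over that same mask.

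**Share of simulated patients in whom the node truly most anticorrelated with the sgACC is picked.** Further assumptions: 20 candidate nodes (chance 1/20 = 0.05), 400 time points, SD 0.15 for individual deviation from the group, a noisy small seed (noise SD 1), and 300 replicates per setting. The Monte Carlo standard error is at most √(0.25/300) = 0.03.

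| Setting | Unweighted mask average | Signed-weighted map | sgACC seed |
|---|---|---|---|
| Shared signal (σ 0.3 or 0.6), m 0 to 0.2, not removed | 0.15-0.52 | 0.54-0.73 | 0.55-0.63 |
| Mean signal removed (σ 0.3; m 0, 0.1, 0.2) | 0.02-0.05 | 0.72-0.80 | 0.52-0.70 |
| No shared signal, m = 0 | 0.11 | 0.75 | 0.67 |
| No shared signal, m 0.05 to 0.2 | 0.74-0.76 | 0.75-0.77 | 0.63-0.66 |

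The unweighted average is below both alternatives in every setting of the first three rows. In the last row it equals the weighted map and beats the seed. Splitting an unweighted mask by sign is not an equivalent repair: with the shared signal present, the positive part reached 0.40-0.62 and the negative part 0.06-0.46.

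**The case against.** The strongest reply is that the protocol does not contradict itself. The scanning section gives the aim, and the mapping section, introduced as the methodology, gives a working proxy: a map seeded from the sgACC through which each patient's signal is read. On that view the intended average is weighted by the map, which is a legitimate proxy and in the simulation usually at least as good as the small seed. The words plain and unweighted are nowhere in the text. Weighting, thresholds and global-signal handling are also often left to an imaging manual, which is not at hand.

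Much of this stands. The unweighted reading is an inference from the words mask, entire and average, and the problem is as much under-specification as contradiction. A reader might infer that the protocol prescribes a plain average and that patients are therefore often stimulated at the wrong site. The documents do not support that: they do not state the weighting, they give no targeting error, and the simulated loss disappears in one plausible range of inputs. A reader might also infer that a null result would say nothing about the hypothesis. That goes too far as well. The trial would still compare MRI-guided placement with the 5-cm rule, and outside the mean-removal case the simulated hit rates stay above chance.

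What does not stand is the appeal to missing detail. The protocol states a rule here, and followed as worded that rule gives a different signal from the one the scanning section and the Background name. A word has to be added to make them agree.

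**Conclusion.** The point holds in conditional form. The protocol has no single reference signal for a step that defines the intervention in the 20 listed targeted patients. The literal reading of step I gives something close to a grey-matter mean.

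Under the assumed inputs, that reading misses the peak named in the scanning section in 48-85% of simulated patients when a shared brain-wide signal is present (1 − 0.52 to 1 − 0.15). It misses it in 95-98% after mean-signal removal. With no shared signal and mean coupling of 0.05 to 0.2 there is no loss against the weighted map. Because the protocol does not say how the global signal is handled, none of these cases can be excluded. The percentages show direction and possible size; they do not estimate what has happened in this trial. The correct site in the simulation means only the peak as the scanning section defines it, and nothing is implied about which site is clinically right.

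**What to change.** Reconcile the Background, the scanning section and steps I and II of the mapping section to one reference time course, written as an explicit formula.

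- If the cohort map is used, state that each patient's time course is averaged with the map's signed values as weights, r(t) = Σ w_v·x_v(t), in place of an unweighted mask average. If that is what was always meant, saying so settles the matter.
- Otherwise, state that the time course of the sgACC sphere is used.
- In either case, say in step II that node time series are correlated with r(t), and state whether and how the global signal is removed.

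The cost is a few lines of protocol text and, if the code differs, one line in the processing script. Enrolment is ongoing and 10 non-responders are reported as enrolled, so the version that produced each target already made should be checked and recorded. That small check is the only real downside.
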